1.0 Synopsis of Study Design/Procedures

This is a prospective, multicenter, open-label study designed to evaluate the early predictive capacity of quantitative Tc 99m tilmanocept planar imaging for downstream clinical response(s) in individuals with moderate to severe rheumatoid arthritis (RA) who are candidates for change in anti-TNF α therapy. Temporal changes (from baseline to 5-weeks) in quantitative imaging will be correlated with longitudinal changes (from baseline to 12 weeks and baseline to 24 weeks) in RA clinical assessments, with the intent of evaluating the clinical utility of Tc 99m tilmanocept for the expedited evaluation of antirheumatic treatment efficacy when compared with longitudinal assessments in clinical practice.

The study objectives are as follows:

Primary:

- To demonstrate that global tilmanocept uptake values (TUV_{global}) obtained before initiation of anti-TNFa therapy (TUV_{global[b]}) and at 5 weeks ± 1 week following change in therapy (TUV_{global[5w]}) has a specificity of greater than 80% to correctly specify a clinical nonresponse to therapy at 24 weeks.
- To demonstrate that TUV_{global} obtained before initiation of anti-TNFα therapy and at 5 weeks ± 1 week following change in therapy has a sensitivity of greater than 65% to correctly classify a positive clinical response to therapy at 24 weeks.

Key Secondary

 To evaluate the negative predictive value (NPV) of TUV_{global} obtained before initiation of anti-TNFα therapy (TUV_{global[b]}) relative to a clinical non-response to therapy at 24 weeks.

Secondary

- To evaluate the sensitivity and specificity of TUV_{global} obtained before initiation of anti-TNF α therapy and at 5 weeks ± 1 week following change in therapy relative to a positive clinical response or a non-response to therapy at 12 weeks.
- To evaluate the NPV of TUV_{global[b]} relative to a clinical non-response to therapy at 12 weeks.
- To evaluate the positive predictive value (PPV), NPV, and overall accuracy (OA) of TUV_{global} obtained before initiation of anti-TNF α therapy and at 5 weeks ± 1 week (Δ TUVglobal_[5w]) following change in therapy relative to a positive clinical response or a non-response to therapy at 12 and/or 24 weeks.
- To evaluate the qualitative assessment of Tc 99m tilmanocept imaging to predict clinical response or non-response following a change in anti-TNFα therapy.

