- To evaluate the additive effect of either quantitative or qualitative assessment of Tc 99m tilmanocept imaging to the other at baseline and change from baseline to 5 weeks \pm 1 week to predict clinical response or non-response following a change in anti-TNF α therapy.
- To evaluate the correlation of changes in TUV_{global} obtained before initiation of anti-TNFα therapy and at 5 weeks ± 1 week following a change in therapy with changes in composite clinical assessments and their constituent parameters at 12 and/or 24 weeks.
- To evaluate the correlation of changes in TUV_{global} obtained before initiation of anti-TNF α therapy and at 5 weeks ± 1 week following a change in therapy with changes in clinical assessments at 12 and/or 24 weeks for specific anti-TNF α bDMARD agents.
- To evaluate the ability of changes in TUV_{global} obtained before initiation of anti-TNF α therapy and at 12 weeks ± 1 week following change in therapy to accurately predict a clinical response or non-response at 24 weeks.
- To evaluate the correlation of changes with TUV_{global} and changes in clinical RA assessments as a means to monitor therapy.
- To evaluate sensitivity and specificity in patient subgroups.

• To evaluate the safety of IV-administered tilmanocept radiolabeled with Tc 99m.

The statistical endpoints that address these objectives are defined in Section 4 (efficacy) and Section 5 (safety). Refer to Section 2.2.1 for subgroup definitions and considerations.

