1.3 Sample Size

NAV3-33 is sized with respect to achieving specified goals in the co-primary endpoints of sensitivity and specificity of $\Delta TUV_{global[5w]}$ with bucketing. Sensitivity and specificity require knowledge of the patient's clinical status at Week 24, and so hypothesis testing will be performed after classification. The value of $\Delta TUV_{global[5w]}$ necessary to predict response vs. non-response and the value of $TUV_{global[5w]}$ necessary to predict response vs. non-response and the value of TUV_{global[b]} at baseline necessary to predict non-response will be determined in advance. The classification procedure occurs in two stages, following the baseline image acquisition and (possibly) following the 5 week image acquisition and calculation of $\Delta TUV_{global[5w]}$. After the baseline imaging, patients whose TUV_{global[5w]} is available, patients whose TUV_{global[b]} is ≥ 5 and D% is $\leq -10\%$ are predicted to be responders. All other patients are predicted to be non-responders. The Week 24 ACR50 will be used as the primary determination of clinical response for the reference standard

The hypotheses for the co-primary endpoints to be tested are:

$$H_{O1}: \pi_{Sp} \le 0.8$$

 $H_{A1}: \pi_{Sp} > 0.8;$

And

 $H_{02}: \pi_{Se} \le 0.65$ $H_{A2}: \pi_{Se} > 0.65.$

In the above π_{Sp} represents the true specificity of the classification procedure and π_{Se} represents the true sensitivity of the classification procedure when used to predict the outcome of the anti-TNF α bDMARD inhibitor therapy at 24 weeks. An overall two-tailed Type I error rate of 0.05 (one-tailed 0.025) was used without adjusting for multiple endpoints, as both co-primary endpoints must be achieved in order to have a successful study. If the actual specificity is 0.92 and the actual sensitivity is 0.8, and if an exact binomial test is used to test the above hypotheses, a total of 98 clinical non-responders and 100 clinical responders are needed for 90% power of the individual tests. That is, a minimum of 198 total patients is needed. This applies to a single reader.

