2.3 Missing Data Conventions

In the statistical analysis of the primary efficacy endpoints of the study, missing data will be handled according to the following table of missing data scenarios:

Variable	Scenario	Primary Imputation Rule	Secondary Imputation Rule
Clinical Status at Week 24	Patient discontinued anti-TNFα therapy prior to Week 24 due to non- response to therapy	Patient classified as a clinical non- responder	N/Ă

Clinical Status at Week 24	Patient discontinued study for reasons not attributable to non-response	Clinical status set to missing	Impute mean clinical response*
TUV Prediction	Patient has TUV _{global[b]} that is ≥ 5 but is missing week 5 imaging data	Impute mean prediction**	Prediction is Y (patient has improved)
TUV Prediction	Patient is missing TUV _{global[b]}	Prediction set to missing	N/A

*Mean clinical response will be calculated as follows: calculate the proportion of unique patients whose clinical status is Y (patient is a clinical responder), randomly allocate this proportion of "Y" to the missing clinical status at week 24 values. Assign all other missing clinical status values "N" (patient is clinical non-responder).

**Mean prediction will be calculated as follows: using the patients for whom $TUV_{global[b]} \ge 5$, calculate the proportion whose TUV prediction is Y (patient has improved), randomly allocate this proportion of "Y" to the missing TUV predictions. Assign all other missing TUV predictions "N" (patient has not improved).

To assess the appropriateness of the missing data conventions for clinical status at week 24 and TUV prediction using mean imputation, tipping point analyses will be performed. Specifically, 95% confidence intervals for sensitivity and specificity will be plotted against increasing proportions of missing values imputed as "Y" to see at what point the conclusion of the study is reversed.

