Х	Improved	xxx (xxx%)	xxx (xxx%)	xxx (xxx%)	PPV	XXXX
					Confidence Limits	(XXXX, XXXX)
					p-value	X.XXXX
	Not Improved	xxx (xxx%)	xxx (xxx%)	xxx (xxx%)		
					NPV	XXXX
	Total	xxx (xxx%)	xxx (xxx%)	xxx (xxx%)	Confidence Limits	(XXXX, XXXX)
					p-value	X.XXXX
					OA	XXXX
					Confidence Limits	(XXXX, XXXX)

 a p-values for PPV testing Ho: π = 0.65 and for NPV testing Ho: π = 0.7. STATKING Clinical Services (DD-MMM-YYYY) Source Program: xxxxxx.sas

Within each part, the above will be displayed for each reader. This format repeats for Part 2 (ACR50), Part 3 (ACR70), Part 4 (CDAI), Part 5 (DAS28), and Part 6 (HAQ-DI). Full table format repeats for PP population (table 22) and for tables 23 – 28.

Table 29. Kendall Rank Correlation of ΔTUV, ΔCDAI, ΔACR Response Criteria Components, and ΔDAS28 with ΔTUV at 5 Weeks Navidea Biopharmaceuticals - Study No. NAV3-33 ITD Population (N=xxx)

Part 1 of 3: Reader x

	Component		Kendall	95% Confidence			Standard
Measure ^a	Parameter	Time Point	Correlation ^b	Limits ^c	n	Mean	Deviation
Δ TUV		5 Weeks			XXX	XXXXXX	XXXXXX
Δ TUV		12 Weeks	X.XXX	(x.xxx, x.xxx)	XXX	XXXXXX	XXXXXX
		24 Weeks	x.xxx	(x.xxx, x.xxx)	XXX	XXXXXX	XXXXXX
Δ CDAI	Overall	5 Weeks	X.XXX	(x.xxx, x.xxx)	XXX	XXXXXX	XXXXXX
		12 Weeks	X.XXX	(x.xxx, x.xxx)	XXX	XXXXXX	XXXXXX
		24 Weeks	X.XXX	(x.xxx, x.xxx)	XXX	XXXXXX	XXXXXX
Δ CDAI	XXXXXXXX	5 Weeks	X.XXX	(x.xxx, x.xxx)	XXX	XXXXXX	XXXXXX
		12 Weeks	X.XXX	(x.xxx, x.xxx)	XXX	XXXXXX	XXXXXX
		24 Weeks	X.XXX	(x.xxx, x.xxx)	XXX	XXXXXX	XXXXXX
Δ ACR	XXXXXXXX	5 Weeks	X.XXX	(x.xxx, x.xxx)	XXX	XXXXXX	XXXXXX
		12 Weeks	X.XXX	(x.xxx, x.xxx)	XXX	XXXXXX	XXXXXX
		24 Weeks	x.xxx	(x.xxx, x.xxx)	XXX	XXXXXX	XXXXXX
Δ DAS28		5 Weeks	X.XXX	(x.xxx, x.xxx)	XXX	XXXXXX	XXXXXX
		12 Weeks	x.xxx	(x.xxx, x.xxx)	XXX	XXXXXX	XXXXXX
		24 Weeks	x.xxx	(x.xxx, x.xxx)	XXX	XXXXXX	XXXXXX

^a Change in ACR will be evaluated through the following components of the ACR Response Criteria: swollen joint count, tender joint count, patient assessment, physician assessment, pain scale, disability/functionality questionnaire, and acute phase reactant (ESR).

 $^{
m b}$ Kendall rank correlation between Δ TUV at 5 weeks and the indicated measurement and time point.

 $^{\circ}$ Confidence limits calculated using Fisher's Z-transformation.

STATKING Clinical Services (DD-MMM-YYYY)

Source Program: xxxxxx.sas

Table format is repeated for each reader. Entire table (all parts) is repeated for the PP population (table 30).

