Data Listing 29. Qualitative plus Quantitative Assessments which differ from Original Quantitative Assessment Navidea Biopharmaceuticals - Study No. NAV3-33 Safety Population (N=xxx)

		Qualitative plus Quantitative	Date/Time of Qualitative plus Quantitative	Original Quantitative	Date/Time of Original Quantitative
Patient No.	Reader No.	Assessment ^a	Assessment	Assessment ^a	Assessment
XXXX	x	XXXXXXX	xxxxxxx/	XXXXXX	 xxxxxxxx/
			XXXX		XXXX
XXXX	х	XXXXXXX	xxxxxxxx/	XXXXXX	xxxxxxxx/
			XXXX		XXXX

^a Assessment is either "Improved" or "Not Improved." STATKING Clinical Services (DD-MMM-YYYY) Source Program: xxxxxx.sas

Data Listing 30. ACR Response Criteria Data Listing Navidea Biopharmaceuticals - Study No. NAV3-33 Safety Population (N=xxx)

Patient		Highest ACR Response	Number of Tender	Number of Swollen	Patient Global	Physician Global		VAS Pain	
No.	Visit	Assessment ^a	Joints	Joints	Assessment	Assessment	HAQ Total	Score	ESR
XXXX	XXXXXXX	XXXXX	XXX	XXX	XXX	XXX	XXX	XXX	XXX
XXXX	XXXXXXX	XXXXX	XXX	xxx	xxx	XXX	XXX	XXX	XXX

^a Options are None, ACR20, ACR50, or ACR70. Response assessment will be blank for baseline measurements. STATKING Clinical Services (DD-MMM-YYYY) Source Program: xxxxxxx.sas

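### The additive-effect objective has no paired estimate: calls that change when the qualitative read is added are listed without outcome, and no output gives the change in sensitivity and specificity with an interval

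*SAP*

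**What the plan says.** SAP Section 1.0 lists this secondary objective: "To evaluate the additive effect of either quantitative or qualitative assessment" of the imaging to the other, at baseline and for the change to Week 5. Protocol Section 2.3 has the same objective. Four sets of output bear on it.

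- **Tables 11-14** report the TUVglobal change rule (bucketing) against each clinical criterion, by reader, with sensitivity, specificity, PPV, NPV and overall accuracy (OA).
- **Tables 25-28** report the combined (qualitative plus quantitative) call against the same criteria. They use the Table 21 shell: "Full table format repeats for PP population (table 22) and for tables 23 – 28". That shell shows the cell counts but reports only PPV, NPV and OA. SAP Section 4.2.3 names the same three measures for the qualitative read.
- **Tables 35-38** come from a logit mixed model of response status. The fixed terms are the quantitative and the combined call; the random terms are subject and reader within subject.
- **Data Listing 29**, "Qualitative plus Quantitative Assessments which differ from Original Quantitative Assessment", shows patient, reader, the two calls and their dates and times. It has no outcome column.

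The table list in SAP Section 7.0 contains no cross-tabulation of the rule against the combined call. On missing data, SAP Section 2.3 begins: "In the statistical analysis of the primary efficacy endpoints of the study, missing data will be handled according to the following table". It imputes a missing Week 5 prediction when baseline TUVglobal is 5 or more. It gives no rule for a missing qualitative or combined read.

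**The concern.** Both calls come from the same reader on the same patient. Where they agree, the pair says nothing about the difference between them. The information on added value lies in the calls that differ. Among ACR50 responders, a changed call either corrects a miss or spoils a hit; among non-responders it either removes or creates a false positive. The change in sensitivity and specificity, and its precision, depend on those counts within each outcome class.

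The planned analysis of the additive effect does not supply this, for three reasons.

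- The mixed model returns conditional log-odds, which do not translate into a change in sensitivity or specificity.
- It has no term for the qualitative read alone, so the reverse direction of the objective, quantitative added to qualitative, is not modelled.
- Its response is identical in all three reader records of a patient while a subject random effect is fitted. That pushes the subject variance upward and leaves the scale of the coefficients poorly determined.

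Without a prespecified paired table, the claim that the read helps or harms would rest on that model, or on a comparison chosen after the results are seen.

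**Working it through.** **1. The plan's own figures.** SAP Section 1.3 states: "If the actual specificity is 0.92 and the actual sensitivity is 0.8", with nulls of 0.80 and 0.65, one-sided 0.025 and exact binomial tests. The critical value r is the smallest with P(X ≥ r | n, p0) ≤ 0.025; power is P(X ≥ r | n, p1).

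| Endpoint | n | r | Actual alpha | Power |
|---|---|---|---|---|
| Specificity, 0.80 vs 0.92 | 98 | 87 | 0.0158 | 0.908 |
| Sensitivity, 0.65 vs 0.80 | 100 | 75 | 0.0211 | 0.913 |

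The stated 90% power is reproduced. Neither figure sizes the added value of the read.

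**2. Inputs for the illustration.** One reader; 100 responders and 500 non-responders (the SAP's expectation at its 5:1 ratio); rule sensitivity 0.80 and specificity 0.92 (the SAP's planning values). Everything about the combined call is **assumed**, since the documents give no counts: sensitivity 0.85 and specificity 0.87.

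**3. Formulas.** Let b be calls corrected and c calls spoiled within one outcome class of size n.

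- Paired difference: (b - c)/n, with 95% half-width 1.96 × √(b + c - (b - c)²/n) / n.
- Treating the two tables as independent: 1.96 × √(p1(1 - p1)/n + p2(1 - p2)/n).

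**4. What the margins allow.** Among responders the rule is wrong in 20 and the combined call in 15. So b - c = 5, and b can lie anywhere from 5 to 20. Among non-responders the rule is wrong in 40 and the combined call in 65. So c - b = 25, and b can lie anywhere from 0 to 40. The first and last rows of each block below are those extremes.

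| Class | Corrected / spoiled | Difference (points) | Paired 95% CI | Exact McNemar p |
|---|---|---|---|---|
| Responders | 5 / 0 | +5.0 | +0.7 to +9.3 | 0.06 |
| | 10 / 5 | +5.0 | -2.5 to +12.5 | 0.30 |
| | 20 / 15 | +5.0 | -6.6 to +16.6 | 0.50 |
| Non-responders | 0 / 25 | -5.0 | -6.9 to -3.1 | <0.001 |
| | 40 / 65 | -5.0 | -9.0 to -1.0 | 0.02 |

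Worked case, 5/0: 1.96 × √(5 - 25/100)/100 = 0.043. Worked case, 20/15: 1.96 × √(35 - 25/100)/100 = 0.116.

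Treated as independent, the margins give -5.5 to +15.5 for sensitivity and -8.8 to -1.2 for specificity, whatever the split. Even these would be hand calculations, because the shell for Tables 25-28 has no sensitivity or specificity rows.

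**5. Pairing is not always tighter.** In the 20/15 case both calls are right in 65 of 100, below the 0.80 × 0.85 = 0.68 expected under independence. The paired interval is then the wider one. The paired interval is preferable because it reflects the observed agreement; it need not be shorter.

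**6. Patient sets.** Table 13 can include predictions imputed for missing Week 5 scans, and it classifies anyone with baseline TUVglobal below 5 from baseline alone. What Table 27 does with those patients is not stated. A hand subtraction of the two tables is valid only if the sets coincide.

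**The case against.** The combined call is not neglected. It meets the outcome in Tables 25-28 and in the model, where the two fixed terms differ only in patients whose calls differ, so the model does draw on the discordant calls. OA with an interval appears for the rule in Table 13 and for the combined call in Table 27, so the direction of any net change in accuracy will be visible. The cell counts allow sensitivity and specificity to be derived by hand. Listing 29 can be linked to ACR50 status in Listing 30 by patient number. The objective does not define additive effect as a change in sensitivity and specificity. All of this stands.

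A reader might infer more than the documents support:

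- **That changed calls are only listed and never analysed, or that the trial cannot show whether the read helps or harms.** Tables 25-28 and 35-38 and the side-by-side OA contradict this.
- **That readers override the rule, or that a combined call needs both scans.** The SAP does not say how the combined call is formed. Protocol Section 3.1 schedules both scans for every subject, so any mismatch in patient sets is possible but of unknown extent.

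What survives is narrower. The corrected/spoiled split and the paired interval are not planned outputs, and rebuilding them from listings would be a post hoc exercise.

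**Conclusion.** The point holds in this limited form. For a stated secondary objective, the plan has no paired estimate of the change in sensitivity and specificity when one assessment is added to the other, and its only model for the question does not yield that quantity. In the illustration, a 5-point gain in sensitivity carries a half-width anywhere from 4.3 to 11.6 points depending on a split that the planned tables do not show. For a 5-point loss in specificity the range is 1.9 to 4.0 points. These sizes rest on assumed accuracy for the combined call, assumed discordant counts, one reader and complete data. The gap in the outputs does not depend on them. The co-primary and key secondary analyses are unaffected. This should be fixed before outcomes are joined to the reads, but it does not threaten the trial's main conclusion.

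**What to change.** - Add Week 12 and Week 24 ACR50 status to Data Listing 29.
- Add a descriptive table by reader, restricted to patients with both a quantitative and a combined call observed, not imputed. Within ACR50 responders and within non-responders separately, cross-tabulate the quantitative by the combined call and count calls corrected and spoiled. Give the difference in sensitivity and in specificity with a paired 95% CI. Name the interval method: in the 5/0 case the simple interval excludes zero while the exact p is 0.06, so a score interval is safer when few calls change.
- Repeat the table for combined versus qualitative alone, which covers the other direction of the objective.
- State in SAP Section 4.2.3 that this table is the estimate of the additive effect, with no alpha allocated. A McNemar p-value is optional.

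The cost is two listing columns and a small set of tables: 3 readers × 2 comparisons × 2 time points = 12 blocks per analysis population. All come from data already planned, with no extra reads or enrolment.
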